3.8 NOTIFICATION OF PRIMARY PHYSICIAN

The primary treating oncologist for each subject will be notified of successful enrollment in the study and provided with detailed study information regarding the schedule and investigational agents. There is no mandated participation from the primary treating physician, though subjects will be encouraged to maintain their relationship with the primary oncologist through periodic visits. Following study completion, the primary oncologist will be provided a summary of the treatments administered and the outcomes of assessments.

3.9 PAYMENT TO SUBJECTS

No payments will be made to subjects.

3.10 INFORMED CONSENT PROCESS

The site investigator will make certain that an appropriate informed consent process is in place to ensure that potential research subjects, or their authorized representatives, are fully informed about the nature and objectives of the clinical study, the potential risks and benefits of study participation, and their rights as research subjects. The site investigator, or a sub-investigator(s) designated by the site investigator, will obtain the written, signed informed consent of each subject prior to performing any study-specific procedures on the subject. The date and time that the subject signs the informed consent form and a narrative of the issues discussed during the informed consent process will be documented in the subject's case history. The site investigator will retain the original copy of the signed informed consent form, and a copy will be provided to the subject.

The site investigator will make certain that appropriate processes and procedures are in place to ensure that ongoing questions and concerns of enrolled subjects are adequately addressed and that the subjects are informed of any new information that may affect their decision to continue participation in the clinical study. In the event of substantial changes to the clinical study or the risk-to-benefit

ratio of study participation, the site investigator will obtain the informed consent of enrolled subjects for continued participation in the clinical study.

3.11 SUBJECT WITHDRAWAL FOLLOWING STUDY COMPLETION

The final study assessment will be at 30 months post initiation of treatment (18 months following treatment completion) and will consist of a clinical assessment, laboratory, and imaging studies as detailed in the Study Schema (Appendix A) and Section 5.7. After the end of treatment, each subject will be followed for the occurrence of adverse events and ongoing disease response with post-treatment visits and assessments as outlined in detail in Section 5.8. Post-treatment visits will continue until the study formally ends, the patient dies, the patient experiences disease progression requiring an alternative therapy, or the subject voluntarily withdraws prior to study completion.

3.12 SUBJECT WITHDRAWAL BEFORE STUDY COMPLETION

Participants may discontinue study treatment at any time for any reason, and may also be discontinued from study treatment at the discretion of the site investigator should any untoward effects occur. In addition, a participant must be discontinued from study treatment but continue to be monitored in the study for any of the following reasons:

- The participant or participant's legally acceptable representative requests to discontinue study treatment
- Confirmed radiographic disease progression
- Any progression or recurrence of any malignancy, or any occurrence of another malignancy that requires active treatment
- Unacceptable adverse events
- The participant has a medical condition or personal circumstance which, in the opinion of the site investigator and/or Lead PI, placed the participant at unnecessary risk from continued administration of study treatment.
- The participant has a confirmed positive serum pregnancy test
- Noncompliance with study treatment or procedure requirements
- Administrative reasons

3.13 DATA COLLECTION AND FOLLOW-UP ON EARLY TREATMENT TERMINATION SUBJECTS

Subjects who are withdrawn from active treatment due to an AE or an SAE will remain enrolled in the trial for the purposes of tracking ongoing toxicity. Subjects will continue with the usual schedule of follow-up visits as feasible and will be included in the intention-to-treat analysis. Subjects who have voluntarily withdrawn from the active treatment will be asked to continue scheduled evaluations, complete an end-of-study evaluation, and be given appropriate care under medical supervision until the symptoms of any AE resolve or the subject's condition becomes stable.

Subjects who discontinue treatment for reasons other than disease progression will have post-treatment follow-up for disease status until disease progression, initiating a non-study cancer treatment, withdrawing consent, or becoming lost to follow-up. All subjects, including those who withdraw due to disease progression or complete the planned follow-up period, will be followed by telephone until death, withdrawal of consent, or the end of the study.

Subjects may be replaced in the trial as needed to ensure that the required number of evaluable subjects is achieved for the designated statistical analyses as put forth in Section 6.

4 STUDY DRUG

4.1 FORMULATION OF STUDY DRUGS

4.1.1 Formulation of Venetoclax

Venetoclax is available in its commercial formulation as a coated tablet with strength of 10, 50, and 100 mg. Excipients include copovidone, colloidal silicon dioxide, polysorbate 80, sodium stearyl fumarate, calcium phosphate dibasic. The 10 mg and 100 mg tablets' coating contains iron oxide yellow, polyvinyl alcohol, titanium dioxide, polyethylene glycol, and talc. The 50 mg tablet's coating contains iron oxide yellow, iron oxide red, iron oxide black, polyvinyl alcohol, titanium dioxide, polyethylene glycol, and talc.

4.1.2 Formulation of CC-486

Azacitidine has been developed for clinical investigation in strengths of 20, 60, 100, 150, 200, and 300 mg tablets. The oral azacitidine formulations may use any of the following excipients: mannitol USP, silicified microcrystalline cellulose NF, crospovidone NF, magnesium stearate NF, croscarmellose sodium, vitamin E TPGS NF, methacrylic acid copolymer (enteric coating) NF, Opadry coating, triethyl citrate NF, talc USP, hydroxypropyl cellulose NF, and hard gelatin capsule.

4.1.3 Formulation of Obinutuzumab

The manufacturing process of the obinutuzumab drug substance consists of cell culture and purification process. Obinutuzumab is provided as a single 1000 mg dose liquid concentrate with a strength of 25 mg/mL. It is supplied in 50 mL glass vials containing 40 mL of the 25 mg/mL liquid concentrate. In addition to the antibody, the liquid also contains histidine/histidine-HCl, trehalose, poloxamer 188 and water for injection. Water meets the specified limits for "Water for Injections" according to Ph. Eur. monograph and "Water for Injection" according to USP monograph.

4.2 DRUG REGIMEN

4.2.1 Summary of Drug Regimen

4.2.1.1 Summary of Drug Regimen for Dose Finding Cohort

In the dose-finding cohort, there will be three escalating dose levels of the three drug combination, and two optional dose de-escalation levels if needed (see Table 2). Venetoclax will be dosed by mouth once daily on days 1-28 or days 1-10 of each 28-day cycle. CC-486 will be dosed by mouth once daily on days 1-14. The doses and days of administration of CC-486 and venetoclax for each dose level are found in Table 2. Obinutuzumab will be administered intravenously at a fixed dose of 1000 mg on days 1, 8, and 15 of cycle 1, and on day 1 of each subsequent cycle. 12 total cycles will

be completed of venetoclax and CC-486. Obinutuzumab will be administered for 9 total cycles (cycle 1-9) and omitted from cycle 10-12. Definition of DLT is in Section 6.2.1.

Table 2: Levels for dose finding

Dose Level	Venetoclax	CC-486	Obinutuzumab
DL 1	400 mg days 1-28	200 mg days 1-14	1000 mg
DL 2	600 mg days 1-28	200mg days 1-14	1000 mg
DL 3	800 mg days 1-28	200 mg days 1-14	1000 mg
DL -1	400 mg days 1-28	150 mg days 1-14	1000 mg
DL -2	400 mg days 1-10	150 mg days 1-14	1000 mg

[figure not shown]

Figure 3: Treatment plan for dose-finding arm

4.2.1.2 Summary of Drug Regimen for Expansion Cohort

In the expansion cohort, the RPD2 established in the dose-finding cohort will be used. Venetoclax will be taken once daily by mouth at the RP2D every day of a 28-day cycle. CC-486 will be taken once daily by mouth at the RP2D on days 1-14 of a 28-day cycle. Obinutuzumab will be omitted from cycle 1-3. In cycle 4, obinutuzumab will be administered intravenously on days 1, 8, and 15. In cycle 5-12, obinutuzumab will be administered intravenously on day 1 only.

[figure not shown]

Figure 4: Treatment plan for expansion cohort

4.2.2 Administration Details for CC-486 for Expansion Cohort

All efforts should be made to administer CC-486 on all scheduled days. A dose missed earlier in a day can be administered later that day as long as it is taken at least 8 hours before the next scheduled dose. Any missed dose should not be taken beyond the last scheduled day of CC-486 administration

for the cycle, but should be returned by the subject for CC-486 accountability. If vomiting occurs after a dose of CC-486 is administered, that dose should not be made up later that day. The subject should continue with the dosing schedule on the next day and inform the treating investigator about the vomiting event at the next visit.

For the purposes of dose adjustment, unacceptable toxicity will be defined as any treatment related AE that is deemed by the treating investigator to be related to CC-486 and/or to the combination of CC-486 with venetoclax and/or obinutuzumab, and that poses a medical risk or substantial discomfort to the subject including, but not limited to, Grade 3 or 4 hematologic or non-hematologic toxicity. CC-486 dosing may be re-escalated (up to the planned dose level in the dose-finding cohort or the RP2D in the expansion cohort) at the discretion of the treating investigator. See Dose Modification Table 3 and Table 4 in Section 4.2.5.

4.2.3 Administration Details for Venetoclax for Expansion Cohort

The dosing of venetoclax in this trial assumes the drug will be administered with a meal, and patients will be instructed to take venetoclax immediately prior to a meal. On days when venetoclax is taken with CC-486, venetoclax should be given first.

If vomiting occurs within 15 minutes after taking venetoclax and all expelled tablets are still intact, another dose may be given. Otherwise, no replacement dose is to be given. In cases where a dose of venetoclax is missed or forgotten, the patient should take the dose as soon as possible and ensure that the minimal interval between the current dose and the next dose is at least 16 hours in order to avoid excessive drug accumulation after the next dose.

All patients must receive prophylaxis for tumor lysis syndrome (TLS) with antihyperuricemics (e.g., allopurinol or rasburicase) and ensure adequate hydration prior to start of venetoclax therapy (see Section 7.4.1 and Appendix G for further details). If TLS is diagnosed by laboratory criteria only AND resolves within 48 hours, venetoclax may be resumed at the prior dose without adjustment. If TLS is diagnosed by laboratory criteria AND lasts greater than 48 hours before full resolution OR TLS is diagnosed by clinical criteria, the dose of venetoclax should be reduced following Table 4.

For the purposes of dose adjustment, unacceptable toxicity will be defined as any treatment related AE that is deemed by the treating investigator to be related to venetoclax and/or to the combination of venetoclax with CC-486 and/or obinutuzumab, and that poses a medical risk or substantial discomfort to the subject including, but not limited to, grade 3 or 4 hematologic or non-hematologic toxicity. Treatment should be delayed if there is any evidence of infection until the resolution of any infection-related symptoms. After an episode of unacceptable toxicity resolves or after the first episode of an infectious complication which resolves within 3 weeks, venetoclax may be resumed or re-escalated to the prior dose at the discretion of the treating investigator. After a second or greater episode of an infectious complication which resolves within three weeks, the venetoclax dose should be adjusted as shown in Table 3 and Table 4. Treatment with investigational agents should not be resumed after an infectious complication that remains symptomatic for greater than 3 weeks.

Patients who require -azole antifungal prophylaxis will require a dose reduction of 75% or more of the original dose and should not follow the schedule in Table 3. The final dose for patients requiring -

azole prophylaxis will be agreed upon by study investigators on a case-by-case basis. See Section 7.4.4.1 for details.

Obinutuzumab will not be subject to dose adjustment. See Dose Modification Guidelines in Section 4.2.5.

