Anemia ≥ grade 3	 For first instance of grade 3 and 4 anemia, transfuse PRBC's as required If recurs, hold treatment and evaluate etiology (drug-related or not). If drug-related, 	Monitor CBC weekly. No more than 3 dose reductions are allowed If treatment is delayed by more than 6 weeks due to treatment-related toxicity, remove patient from study

decrease by one dose level. • If recurs again, reduce by one additional dose	
level.If recurs again, reduce by one additional dose level.	

Table 3B. Dose Modifications for non-Hematologic Toxicities. See Dose Levels for venetoclax and CC-486 in Table 4.

Observation	Action	Comments
AE resolves promptly with supportive care	Maintain dose level	
Febrile neutropenia or neutropenia with infection	 Withhold all agents until resolution of fever and infection (as applicable) 	
Grade 3 or higher non- hematologic AE that does not resolve to grade 2 or	 Hold venetoclax, CC- 486, and obinutuzumab (if applicable) 	Monitor CBC and CMP weekly.
below within one week despite maximum supportive care	• Resume therapy at same dose level once AE resolves to ≤ grade	No more than 3 dose reductions are allowed
	 If recurs, reduce by one dose level. If recurs again, reduce by one additional dose level. 	If treatment is delayed by more than 6 weeks due to treatment-related toxicity, remove patient from study
	If recurs again, reduce by one additional dose level	

Table 4. Venetoclax and CC-486 Dose Levels to be used if dose modifications are needed as per Tables 3A and 3B in the Expansion Cohort.

Agent	Starting Dose	Dose Reduction #1	Dose Reduction #2	Dose Reduction #3
Venetoclax	RP2D dose and schedule	RP2D dose on Days 1-10 only	50% reduction in dose, on Days 1-10 only	75% reduction in dose, on Days 1-10 only

and schedule same schedule same schedule with every other day dosing
--

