7.4.4.2 Management of Infections

The following guidance is provided for infections that occur during the study:

- Patients with uncontrolled systemic infection are excluded from the trial.
- Blood counts should be closely monitored for evidence of infection throughout the trial.
- All patients should be monitored closely for infection and treated aggressively according to institutional guidelines, including growth factor and transfusion support.
- If grade 2-4 infection occurs, treatment (any or all study treatments) may be delayed for a maximum of 4 weeks after the last dose, regardless of presence or absence of neutropenia. If the infection has not resolved after 3 weeks, study treatment must be discontinued. It is strongly recommended that sites delay study treatment when presented with evidence of infection.

- After the first occurrence of an infection which resolves within three weeks, venetoclax and other study drugs can be resumed at the prior dose. After the second occurrence of an infection that resolves within three weeks, the dose of venetoclax should be adjusted per Section 4.2.3.
- Patients being treated with an -azole antifungal agent must cease study drug administration while under active antimicrobial treatment and must not resume venetoclax until 3 posaconazole half-lives have passed (approximately 96 hours).
- Signs and/or symptoms of infection should result in prompt evaluation and appropriate samples for bacteriological investigation prior to starting antibiotic or other treatment.
- A blood sample should be collected at screening and stored for testing if the patient develops a viral infection on study (e.g., cytomegalovirus, varicella zoster virus, herpes simplex virus, or Epstein–Barr virus).
- Grade 4 infection should be reported to the lead PI expeditiously.

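### If DL -2 becomes the RP2D, Table 4's first venetoclax reduction changes nothing and Section 4.2.1.2 states 28 dosing days instead of 10; Table 3B also omits the second-infection step that Section 4.2.3 cites

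*Combined protocol and SAP*

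**What the plan says.** **Dose levels and RP2D.** Table 2 (Section 4.2.1.1) defines five dose levels. Four give venetoclax on Days 1-28. DL -2 gives 400 mg on Days 1-10 with CC-486 150 mg on Days 1-14. Section 6.2.1 reaches DL -2 only after DLTs at DL -1. It makes DL -2 the RP2D if no patient there has a DLT, or if one does and none of the next three do.

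**Expansion schedule.** Table 4's starting cell for venetoclax is "RP2D dose and schedule". Section 4.2.1.2 instead has venetoclax taken on every day of the cycle, and the Study Summary gives Days 1-28. Neither makes an exception for DL -2.

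**Venetoclax reductions.** Table 4 has three steps: the RP2D dose confined to Days 1-10, then half the dose on those days, then a quarter. Section 4.2.5 allows at most three reductions. For clinical tumor lysis syndrome (TLS), or laboratory TLS lasting more than 48 hours, Section 4.2.3 says "the dose of venetoclax should be reduced following Table 4".

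**Second infection.** For a second or later infection resolving within three weeks, Section 4.2.3 says "the venetoclax dose should be adjusted as shown in Table 3 and Table 4". Section 7.4.4.2 repeats the duty: "After the second occurrence of an infection that resolves within three weeks, the dose of venetoclax should be adjusted per Section 4.2.3". The only row of Table 3B that names infection is headed "Febrile neutropenia or neutropenia with infection". Its action is to withhold everything until fever and infection clear, with no step for recurrence. The row "AE resolves promptly with supportive care" keeps the dose unchanged.

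**The concern.** The venetoclax steps in Table 4 were built for a drug started on a 28-day schedule: the first step shortens the schedule and the later steps cut the dose. From DL -2 there is no schedule left to shorten. A site that reduces venetoclax for TLS or a repeat infection would record a reduction, use one of the three allowed, and give the same dose on the same days.

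The schedule wording matters for the same RP2D. Read literally, Section 4.2.1.2 would put expansion patients back on 28-day venetoclax, the schedule of the level that dose finding had just left because of DLTs.

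The second-infection issue is smaller. An investigator sent to Table 3 for the adjustment does not find it there, and may find a row that points the other way.

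**Working it through.** The plan states no figure on this point. (Its Section 6.1 design figures reproduce exactly: α 0.0997, power 0.8038, early stopping under the null 72.16%. Nothing below affects them.)

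**1. Planned venetoclax per 28-day cycle = daily dose × dosing days.** Doses and days are from Table 2 and steps from Table 4. The percentage cuts are taken as fractions of the RP2D dose; step 1 does not depend on that reading.

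| RP2D | Start (mg) | Step 1 (mg) | Step 2 (mg) | Step 3 (mg) |
|---|---|---|---|---|
| DL 3 | 800 × 28 = 22,400 | 800 × 10 = 8,000 | 400 × 10 = 4,000 | 200 × 10 = 2,000 |
| DL 2 | 600 × 28 = 16,800 | 600 × 10 = 6,000 | 300 × 10 = 3,000 | 150 × 10 = 1,500 |
| DL 1, DL -1 | 400 × 28 = 11,200 | 400 × 10 = 4,000 | 200 × 10 = 2,000 | 100 × 10 = 1,000 |
| DL -2 | 400 × 10 = 4,000 | 400 × 10 = 4,000 | 200 × 10 = 2,000 | 100 × 10 = 1,000 |

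From any 28-day start, step 1 is a real cut: 1 − 10/28 = 64.3%. From DL -2 the three steps cut 0%, 50% and 75%, so only two of the three change anything.

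**2. Where the empty step matters.** The TLS and second-infection rules in Section 4.2.3 direct a change to venetoclax and name no CC-486 step. In those two situations nothing else in the oral regimen moves at step 1.

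**3. Schedule conflict at DL -2.** Read literally, Section 4.2.1.2 gives 400 × 28 = 11,200 mg per cycle, against 400 × 10 = 4,000 mg at DL -2. The ratio is 11,200 / 4,000 = 2.8. With CC-486 150 mg on Days 1-14, this is exactly DL -1's oral regimen.

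**4. A second infection that resolves within three weeks, read against Table 3.**

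- Table 3A reduces the dose if grade 3 or higher neutropenia recurs.
- Table 3B's last row reduces it for a recurrent grade 3 or higher event that has not fallen to grade 2 or below within a week.
- Table 3B's neutropenic-infection row withholds and gives no reduction.
- Table 3B's prompt-resolution row keeps the dose.

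A second infection that is below grade 3, or that settles within a week, and that comes without recurrent grade 3 or higher neutropenia, therefore has no reduction row in Table 3. Table 4, named in the same sentence of Section 4.2.3, does hold the step.

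**Caveat.** In the text copy used here, Table 3B's last row and Table 4's CC-486 row are partly broken. No conclusion rests on the CC-486 row, and the reading of Table 3B should be checked against the formatted protocol.

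**The case against.** **DL -2 is remote, and a review is scheduled.** It needs DLT failure at both DL 1 and DL -1, while Section 1.2.2.1 expects the RP2D at 800 mg venetoclax and 200 mg CC-486. Section 4.2.5 says it will be re-evaluated after phase I, and Section 6.2.2 plans a review of the dose modification plan before expansion, when the RP2D is known. Section 4.2.1.1 treats dosing days as part of each dose level, so the daily wording may be a slip in a summary. This supports a minor rating. It does not remove the defect: Section 6.2.1 permits DL -2, neither review statement commits to these changes, and the note in 4.2.5 does not clearly reach 4.2.1.2 or the Study Summary.

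**The second-infection rule already exists.** This largely stands. A reader might infer that the plan has no dose reduction after a second infection. The documents do not support that: Section 4.2.3 states the duty and names Table 4, and the TLS rule likewise goes straight to Table 4. A reader might also set the 64.3% cut of a full Table 4 step against 0% under the prompt-resolution row and call that the size of the problem. That needs a generic row to override an infection-specific instruction, which is a strained reading, so the contrast is not used. Nor does the grade range in Section 7.4.4.2 ("If grade 2-4 infection occurs, treatment (any or all study treatments) may be delayed") prove that grade 2 infections fall under the reduction rule. That sentence governs delay, and the second-occurrence rule states no grade. What remains is that Table 3, which Section 4.2.3 cites as showing the adjustment, does not show it.

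**Which drug steps down, and whether the cap of three is per drug.** These could be worded more clearly, but they are matters of clarification and not part of this finding.

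**Conclusion.** The DL -2 defect holds exactly, on one condition: that DL -2 is selected as the RP2D. The first venetoclax reduction is then 0% (4,000 to 4,000 mg per cycle). The expansion schedule text would give 2.8 times the DL -2 amount and contradicts Table 4's own starting cell. The documents give no basis for a probability that DL -2 is chosen.

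The second-infection issue holds for any RP2D, but only as a minor inconsistency between Table 3B and Sections 4.2.3 and 7.4.4.2. The documents give no repeat-infection rate, so no patient count is offered.

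A reader might infer that the CR rate or the Simon design is affected. Nothing in the documents supports that; both issues are faults in safety instructions. Severity: minor.

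**What to change.** - **Table 4, footnote:** if the RP2D is DL -2, the first venetoclax reduction is 50% on Days 1-10 and the second is 75% on Days 1-10, with no third venetoclax reduction. The sequence becomes 4,000, 2,000, 1,000 mg per cycle, ending at the same lowest dose as now.
- **Section 4.2.1.2:** replace the daily-dosing phrase with *on the RP2D schedule*. **Study Summary:** add Days 1-10 for DL -2 to the venetoclax regimen line.
- **Table 3B:** replace the neutropenic-infection row with a single row: *Infection or febrile neutropenia: hold all study drugs until cleared. First infection clearing within 3 weeks: may restart at the previous dose. Second or later infection clearing within 3 weeks: lower venetoclax by one Table 4 level. Still symptomatic beyond 3 weeks: stop study treatment (4.2.3, 7.4.4.2). Table 3A still applies to neutropenia.* Add *(other than infection)* to the prompt-resolution row.

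The cost is a few lines of wording. The table edits fit the review already planned before expansion; Section 4.2.1.2 and the Study Summary line need to be added to its scope. Design, sample size and visits do not change.
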